9.5 Consent

Once screening is completed, all eligible youth participants will be invited to review the full PICF and provide their personal consent via the online consent form (see Appendix C). Once this is completed, participants will then be invited to register to the study, creating a secure account on the Black Dog Research Engine. To register, participants are asked to provide their full name, email, mobile phone number and age. They are also asked to create a password to ensure account security. Registered participants will then be invited to view the online parental PISCF (Appendix C) to be completed by their parent or guardian. Participants will be asked to complete and submit the online parent consent form within 14 days. After the parental PICF is submitted by the parent, the young person will be automatically notified by the Research Engine of their confirmed involvement in the study and invited to complete the baseline assessment. A copy of the parental PICF will be emailed to the parent's email address provided. A copy of the personal PICF will also be emailed to youth participants via a URL link included in the study welcome email.

Participants will have sufficient time to consider study participation because they have 14 days to complete their parental PICF. Participants will receive three reminders to return their consent form, sent on day 3, day 5, and again on day 10. Participants who fail to complete the parental consent form will be withdrawn from the study.

Once personal and parental consent has been provided, participants will be sent an automated invitation to complete the baseline assessment. The baseline assessment will remain open for a period of 7 days, allowing participants further time to reconsider their consent after its initial provision. Participants can cease the baseline assessment at any time, which will result in their removal from the study.

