9.6 Withdrawal of Consent or Participant

Participants will be able to withdraw from the study at any time by the following:

- 1) *Emailing the research team:* By emailing [contact] and providing their full name, date of birth, mobile number with the subject line "withdraw" or equivalent.

- 2) *Via the study withdrawal link provided in the initial study welcome email:* By clicking on the URL at the bottom of the welcome email, participants can withdraw at anytime and actively remove all data from the study without making direct contact with the research team.
- 3) *Failure to complete the baseline assessment within 7 days:* Participants who fail to complete the baseline assessment within 7 days will be automatically withdrawn from the study.

Once withdrawn from the research study, all of participants' personal identifiable data (e.g. name, email address, mobile phone number) will be removed and no further information will be collected from them. The research team will retain some information (e.g. age, gender, symptom severity) for trial reporting purposes. Withdrawn subjects will not be recontacted or followed up. However, to ensure participant safety, withdrawn subjects will be able to report whether their withdrawal from the study was associated with adverse events related or unrelated to the study activities. Participants who actively withdraw will be informed that they can, if they wish, provide feedback about any study activities but there is no obligation to do so.

Failure to complete the primary and secondary endpoint assessments will be considered lost to follow-up for that timepoint but will not withdraw participants from the study. Participants who fail to download or access the study interventions during the study period will not be withdrawn from the study. Withdrawn subjects will not be replaced as the sample size calculations accounts for study attrition.

10. Treatment of Subjects

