

is unable to be contacted by phone after two attempts, they will be sent an email from the study email address informing them of the attempt to make contact. This email will also contain mental health information and support services.
 
c) A register of these events and associated interactions (i.e., telephone call attempts, times, dates, outcomes) will be recorded in a separate risk management spreadsheet managed by the Trial Manager. These events will also be recorded in the UNSW Safety Monitoring Template.
	
Effect/Event	Criteria

Mental health related hospitalisation reported at primary or secondary endpoint or disclosed in any other study procedures (e.g. call back phone calls, participant emails).
	
Participants reports yes to the item “Throughout the study, have you had any mental health problems where you had to go to a hospital emergency department, or had to stay in hospital for more than one day?” in the primary and secondary endpoint study assessments, or, reports this event via other study procedures and activities.

Action	

All relevant study data for this event will be recorded in the UNSW Safety Monitoring Template for reporting.
	
Effect/Event	Criteria

Self-identified deterioration in mental health due to study activities reported by participants at primary or secondary endpoints.
	
Participants reports yes to the item “At any point throughout the study, did you feel that any of the study activities made your mental health or feelings of depression, anxiety or suicidality worse?” in the primary and secondary endpoint assessments, or, reports this event via other study procedures and activities.

Action	

All relevant study data for this event will be recorded in the UNSW Safety Monitoring Template for reporting.
	

b) Known Harms, Risks or Discomforts

The interventions evaluated in this trial have been designed and reviewed by mental health professionals to support young people to manage their mental health. The researchers do not anticipate significant harm or distress related to use of the interventions in the current trial, however, the following harms, risks or discomforts may occur:

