11.3 Serious Adverse Events

Serious Adverse Events (SAEs) that result in or lead to one or more of the following and the event is **not related** to the trial intervention:

- The death of a trial participant.
- A life-threatening illness or injury involving a trial participant.
- A participant's permanent impairment of body structure or body function.
- In-patient or prolonged hospitalisation (not for a pre-existing condition or an elective surgery) of a trial participant.
- Medical or surgical intervention to prevent life-threatening illness or injury or permanent impairment to a body structure or function of a trial participant.
- Fetal distress, fetal death or congenital abnormality or birth defect.

SAE reports are classified following the safety assessment flowchart and are assessed by Sponsors Independent Medical specified in section 2 of the protocol. The Sponsors Independent Medical cannot delegate this responsibility to other research personnel. SAR reports must be recorded in the [UNSW Safety Monitoring Register Template](#).

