Prior to recruitment commencing, the TMG members will form an understanding of the protocol and study endpoints. The TMG will be provided with a monthly report on safety events and will convene a meeting after the baseline, primary endpoint (6-weeks post-baseline) and secondary endpoint (4-months post baseline) assessments have been completed to review the UNSW Safety Monitoring Template, which includes the number of call backs that were triggered, and the follow-up that was carried out. Meetings will be held face-to-face if practicable, or otherwise by video conference. Prior to each meeting, a report will be sent to the TMG outlining any recommendations and rationales.

Reporting

For this current trial, an adverse event (AE) is defined as any untoward medical or clinical occurrence in a participant without regard to the possibility of a causal relationship. A register of these events and associated interactions will be recorded in a separate risk management spreadsheet managed by the Trial Manager. These events will also be recorded in the UNSW Safety Monitoring Template.

A serious adverse event (SAE) for this trial is defined as any untoward occurrence that involves hospitalisation or death (suicide or otherwise). As per the NHMRC Safety Monitoring and Reporting Guidelines, any suspected unexpected SAEs or reactions will be reported to the TMG and the UNSW Human Research Ethics Committee within 24 hours of the research team becoming aware, using the Adverse Event Form provided by the UNSW HREC. All AEs, both solicited and spontaneous, will be reported to the TMG.

A breach of protocol is defined as something likely to affect the rights and safety of a trial participant (for example, the sharing of data to those outside those with approved access), or the reliability or robustness of the data is compromised. Any serious breaches of protocol will be reported to the TMG and UNSW HREC within 24 hours of the research team becoming aware, using the Suspected Serious Breach Report Form.

Confidentiality

All information and data provided to the TMG will be considered privileged and confidential. The TMG will agree to use these data to accomplish the responsibilities of the TMG and will not use it for any other purpose without written consent from the Chief Investigator or trial sponsor.

Safety analyses

The primary safety endpoints are:

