Appendix J: Standard operating procedures

The MobiliseMe study: Testing different smartphone activities to help improve young people's mental health

Trial Management Group

Version 1 (25th October 2021)

Procedures for eliciting reports of and for recording and reporting adverse event and intercurrent illnesses.

Adverse Events and Serious Adverse Events

For this current trial, an adverse event (AE) is defined as any untoward medical or clinical occurrence in a participant without regard to the possibility of a causal relationship. All AEs will be collected after a participant has consented and enrolled into the trial. AEs may include severe suicidal ideation as reported on baseline, primary or secondary endpoint online self-report assessment. Severe suicidal ideation will be defined as self-reports of suicidal thoughts or thoughts of self-harm More than half the days or Nearly every day, indicated by a score of ≥ 2 on item-9 of the PHQ-9. AEs also include severe depressive symptoms reported by participants at the final assessment (secondary endpoint) before trial ends. Severe depressive symptoms are indicated by a total score ≥ 20 on the Patient Health Questionnaire-9 at secondary endpoint assessment (i.e., 4-months post-baseline). Finally, AE also include mental health related hospitalisation reported at primary or secondary endpoint or disclosed in any other study procedures (e.g. call back phone calls, participant emails).

A serious adverse event (SAE) for this trial is defined as any untoward occurrence that involves hospitalization or death (suicide or otherwise) without regard to the possibility of a casual relationship.

Adverse Reactions (AR) are considered untoward and unintended responses to the trial intervention related to any intervention procedures. AR may include self-identified deterioration in mental health due to study activities reported by participants at primary or secondary endpoints.

Reporting Adverse Events

The trial will maintain a record of any reported adverse events or serious adverse events. A summary of adverse events will be reported to the trial's qualified expert (as named in Section 1). A summary of serious adverse events will be reported annually to the UNSW sponsors delegate and UNSW ethics committee.

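### SAEs are defined as any hospitalisation or death, but the only hospital question shown covers mental health problems, so other admissions and all deaths depend on unsolicited reports

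*Protocol*

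**What the plan says.** **Definition.** Appendix I (Reporting): "A serious adverse event (SAE) for this trial is defined as any untoward occurrence that involves hospitalisation or death (suicide or otherwise". Appendix J gives the same scope: "any untoward occurrence that involves hospitalization or death (suicide or otherwise) without regard to the possibility of a casual relationship". Section 11.3 has a longer list that includes death and "In-patient or prolonged hospitalisation (not for a pre-existing condition or an elective surgery) of a trial participant". None of the three restricts an SAE to mental health causes.

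**Ascertainment.** The hospital item in Section 11.1 asks about the study so far: "have you had any mental health problems where you had to go to a hospital emergency department, or had to stay in hospital". A stay counts only if it exceeds one day. The item is asked "in the primary and secondary endpoint study assessments, or, reports this event via other study procedures and activities". The other routes named for this event, such as call-back calls and participant emails, are also written for mental health hospitalisation. A second safety item asks whether study activities made the participant's mental health worse; it does not ask about admissions. Appendix I adds that spontaneous as well as solicited adverse events go to the Trial Management Group (TMG).

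**Non-response.** Section 9.6: "Failure to complete the primary and secondary endpoint assessments will be considered lost to follow-up for that timepoint", without withdrawal from the study. Section 10 gives each assessment a 7-day window and two reminders. Withdrawn participants are not followed up, but may report an adverse event connected with their withdrawal.

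**Oversight.** Appendix J says that no data and safety monitoring committee will be convened and that the TMG does all monitoring. Appendix I lists four primary safety endpoints, and death is not among them.

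**The concern.** The definition covers all causes, while the question asked covers one. A participant admitted after an injury or with a physical illness has an SAE by Appendices I and J, but nothing shown asks about it. A death cannot be self-reported, and no route for learning of one is described. Without a volunteered report, a death would look like a missed survey.

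Appendix J presents itself as the procedure for eliciting adverse events and intercurrent illnesses, and says that all adverse events will be collected after enrolment. The collection described is narrower than that. A reader of the final report could take the SAE count as all-cause when it is mostly self-reported mental health hospital use. The TMG would have the same incomplete picture when it advises on continuing, modifying or stopping the trial.

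There is also a comparative problem. Where events depend on being volunteered, the arm with more staff contact has more chances to volunteer them.

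**Working it through.** The protocol states no SAE rate or expected count, so there is no figure to reproduce. The check compares definition with ascertainment and then uses labelled assumptions to show what can and cannot be said about size.

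**Step 1. Event type against route.**

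| Event within the SAE definition | Actively asked? | Other route described |
|---|---|---|
| Mental health admission | Yes, at 6 weeks and 4 months, looking back over the study | Calls, emails, other procedures |
| Admission for another reason | No item shown | Spontaneous report only |
| Death | Cannot be self-reported | Spontaneous report only (by a third party) |

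The item also fits the word hospitalisation loosely. It counts an emergency visit without admission, and it misses a stay of one day or less that did not begin in an emergency department.

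**Step 2. Who is asked.** Section 8 gives 489 participants and 20% attrition to the primary endpoint. 489 × 0.80 = 391 are asked at 6 weeks and 489 × 0.20 = 98 are not. Those 98 are invited again at 4 months, and the item looks back over the whole study, so 98 is not the number with unknown final status. That number is the participants who answer neither survey. The protocol does not state it, because it gives no 4-month attrition.

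**Step 3. Does a near-zero count follow?** Expected solicited events = 489 × response × rate, and P(0) = (1 − rate)^n. Rates of mental health hospital use and the 60% response are assumptions; 80% is the planned 6-week figure.

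| Assumed rate | Expected at 80% response | P(0) | Expected at 60% response | P(0) |
|---|---|---|---|---|
| 0.5% | 2.0 | 14% | 1.5 | 23% |
| 1% | 3.9 | 2% | 2.9 | 5% |
| 2% | 7.8 | <0.1% | 5.9 | 0.3% |
| 5% | 19.6 | <0.1% | 14.7 | <0.1% |

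So a near-zero count does not follow from the method.

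**Step 4. What share of SAEs could the item pick up?** Share = (mental health share of SAEs) × (response). With assumed shares of 25–75% and response of 60–80%, the lowest value is 0.25 × 0.60 = 15% and the highest is 0.75 × 0.80 = 60%. Spontaneous reports come on top and cannot be quantified.

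**Step 5. Contact by arm.** Section 10.1 gives arm 2 six weekly SMS chats with research staff. Arms 1 and 3 have no human contact beyond technical support by email. The opportunity to mention an unsolicited event is therefore unequal during the six-week intervention period. Nothing in the document shows how large the resulting difference would be.

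**The case against.** The strongest reply is that the plan does more than the SAE wording suggests. The SAE type most expected in this population is asked about twice, with a look-back over the whole study. Disclosure by call, email or other procedures is accepted, spontaneous adverse events reach the TMG, and withdrawn participants can report. The stopping guideline is expressly not confined to the listed endpoints. All of this stands.

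It rules out three stronger readings that a reader might infer:

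- **That a near-zero SAE count is built in.** Step 3 shows otherwise, and the protocol gives no rate from which to argue it.
- **That events are captured only in those who answer the surveys.** The other routes contradict this.
- **That serious-event status is unknown for one participant in five.** This would need everyone who misses week 6 also to miss month 4, which nothing in the document says.

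It is also fair to say that the full assessments (Appendix D) are not reproduced in the copy available, and that a mental health care questionnaire is listed without its wording. The point therefore concerns the only hospital item visible.

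The reply does not close the gap. None of these routes actively asks about an admission for another reason, and none is a described means of learning of a death. Accepting spontaneous reports is different from seeking them.

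**Conclusion.** The point holds as a mismatch between the SAE definition and its ascertainment. Appendices I and J promise an all-cause count, and the visible procedure solicits one cause. SAEs will be under-ascertained by an amount that the document does not allow one to fix. The 15–60% range in Step 4 is illustrative and rests on the assumed mental health share and response. A difference between arms in volunteered reports is possible, not demonstrated.

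The practical consequence is for interpretation: a low or zero count of deaths or other admissions could not be read as evidence of all-cause safety. The primary efficacy analysis is unaffected. The conclusion assumes that Appendix D holds no further hospital item, which the sponsor can check at once.

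**What to change.** 1. Reword the hospital item at both follow-up assessments to ask about any emergency department visit or hospital stay, for any reason, since the study began. Follow it with: was this for a mental health problem? The first part serves the SAE definition and the second keeps the mental health hospitalisation endpoint.

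2. State in Appendices I and J that deaths, and events in participants who answer neither follow-up survey, are captured by spontaneous report only, so that a zero is not read as all-cause safety.

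The cost is one slightly longer item and an ethics amendment, with no extra staff, visits or participants.

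An automated enquiry to parents of non-responders may look like a natural addition, because a parent email address is held from consent. It is not proposed here. Section 11.1 and Appendix J limit contacting parents about risk to cases where confidentiality has to be broken or the participant asks for it, and a routine email would cut across that limit.

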9.2 Exclusion Criteria

At the time of screening, participants will be excluded if they are:

- Currently experiencing severe suicidal ideation (as determined by a score of ≥ 2 on item 9 of the self-report Patient Health Questionnaire-9-Adolescent version).
- Had serious suicidal ideation in the past month (as determined by self-report).
- A suicide attempt in the past month (as determined by self-report).
- Experiencing nil or severe depressive symptoms (as determined by a score total of ≤ 4 or ≥ 20 on the self-report Patient Health Questionnaire).
- Currently receiving OR about to start (in the next 2 weeks) any psychological treatment for feelings of low mood or depression from a psychologist, psychiatrist or other mental health professional
- Currently taking OR about to start (in the next 2 weeks) any daily prescribed medication (e.g., anti-depressants) for their mental health (low mood, depression or anxiety).

- Unable to gain parental consent to participate (as determined by failure to return parental consent form within their recruitment period).
- Located outside of Australia, not within age range or fail to satisfy any of the other inclusion criteria (as determined by the self-report screener).

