11.1 Assessment of Safety Event Report Forms

Safety reports will be assessed on the seriousness, causality, and expectedness of the event to the trial treatment(s), intervention(s), investigational medical product(s), investigational medical device(s). The following are known and expected adverse effects, harms, risks or discomforts associated with trial procedures, treatments or interventions.

a) Known Adverse Effects

Effect/Event	Criteria
Frequent, current suicidal ideation (i.e., thoughts of death or of harming oneself) detected through the self-report Patient Health Questionnaire-9, at baseline, primary or secondary endpoint.	A participant reports an item score of ≥ 2 (“More than half the days” to “Nearly every day”) on item 9 of the PHQ-9 (i.e., “Over the last two weeks, how often have you had thoughts that you would be better off dead, or of hurting yourself in some way?”)
Action	

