- Frequent, current suicidal ideation (i.e., thoughts of death or of harming oneself, score greater than 2 on item 9) detected through the self-report Patient Health Questionnaire-9 at primary or secondary endpoint.
- Severe depressive symptoms detected at final study assessment (i.e., secondary endpoint: 4-months post-baseline) through the self-report Patient Health Questionnaire-9.

- Mental health related hospitalisation reported at primary or secondary endpoint or disclosed in any other study procedures (e.g. call back phone calls, participant emails).
- Self-identified deterioration in mental health due to study activities reported by participants at primary or secondary endpoints.

Stopping guidelines

The primary charge of the TMG is to monitor the study for participant safety. As such, the TMG may recommend pausing or terminating the trial if they have concerns for participant safety, based on (but not limited to) a higher than anticipated rate for one or more of the primary endpoints.

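### Appendix I sets the suicidal-ideation safety endpoint at item 9 above 2, where the rest of the protocol uses 2 or more; Appendix J allows 7 days for an urgent safety measure notice that Section 11.6 limits to 72 hours

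*Protocol*

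**What the plan says.** **Item 9 threshold.** Four places in the protocol set a cut-off on item 9 of the PHQ.

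- Appendix I, Safety analyses, names as a primary safety endpoint "Frequent, current suicidal ideation (i.e., thoughts of death or of harming oneself, score greater than 2 on item 9", assessed at the primary and secondary endpoints.
- Section 11.1 lists "Frequent, current suicidal ideation (i.e., thoughts of death or of harming oneself) detected through the self-report Patient Health Questionnaire-9" as a known adverse effect. Its criterion is "A participant reports an item score of ≥ 2", and it spells out that this spans the two most frequent response categories.
- Appendix J defines severe suicidal ideation as an adverse event "indicated by a score of ≥ 2 on item-9 of the PHQ-9", naming the same two categories.
- Section 9.2 excludes anyone "Currently experiencing severe suicidal ideation (as determined by a score of ≥ 2 on item 9".

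Under Stopping guidelines, Appendix I lets the Trial Management Group advise a pause or an early end on safety grounds. The basis it names is the event rate: "based on (but not limited to) a higher than anticipated rate for one or more of the primary endpoints".

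**Notification limit.** Section 11.5 gives 15 calendar days to notify the ethics committee and the sponsor's delegate of any significant safety issue. Section 11.6 shortens this to 72 hours when an urgent safety measure is needed. Appendix J, under Reporting Adverse Events, covers the same event and the same two recipients. It asks for a prompt report but sets the outer limit at 7 days.

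**The concern.** The first mismatch changes who counts toward a safety endpoint. Appendix I and Section 11.1 use the same label for two different sets of participants. Someone scoring exactly 2 at 6 weeks or 4 months meets the Section 11.1 criterion, is offered a call-back and is entered in the safety register, yet does not meet the endpoint in Appendix I. If both texts are followed literally, the Trial Management Group has one count in its safety template and a smaller one in the endpoint rate, under one name. That endpoint rate is the one its stopping guideline points to. The trial has no separate data and safety monitoring committee, so this group is the only monitoring body.

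The second mismatch leaves two outer limits for one notification. A team working from Appendix J, which is headed as the standard operating procedures, could comply with it and still breach Section 11.6.

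**Working it through.** No statistical calculation applies. The check sets the texts side by side.

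**Step 1: which item 9 scores each text counts.** The item is scored in whole numbers. Section 11.1 and Appendix J both state that a cut-off of 2 or more covers the two highest response categories, which are scores 2 and 3.

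| Place | Use | Rule | Scores counted |
|---|---|---|---|
| Section 9.2 | exclusion at screening | ≥ 2 | 2, 3 |
| Section 11.1 | adverse effect, pop-up, call-back offer, register | ≥ 2 | 2, 3 |
| Appendix J | adverse event definition | ≥ 2 | 2, 3 |
| Appendix I | primary safety endpoint | > 2 | 3 |

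Appendix I counts one category where every other item 9 rule counts two. The closest comparison is Section 11.1 against Appendix I, because they share the label. Section 9.2 and Appendix J call the same cut-off severe ideation, so they are supporting context.

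**Step 2: is there an innocent explanation?** The Appendix I threshold is written in words, so no symbol was lost when the PDF was read. It is current text, not an amendment log. Appendices I and J carry the same version number and date (Version 1, 25 October 2021), so a later revision of one does not explain the difference. The protocol fixes the definition itself and does not leave it to a statistical analysis plan.

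**Step 3: what follows for monitoring.** At each follow-up, let n2 and n3 be the numbers scoring 2 and 3. The register count under Section 11.1 is n2 + n3 and the Appendix I endpoint count is n3, so the difference is n2. The protocol gives no item 9 distribution, so n2 cannot be estimated and no percentage is offered.

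**Step 4: the notification limits, in hours.**

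- Section 11.6, urgent safety measure: 72 h.
- Appendix J, the same event and recipients: 7 × 24 = 168 h.
- Section 11.5, significant safety issues in general: 15 × 24 = 360 h.

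The Appendix J limit is 168 − 72 = 96 h longer than Section 11.6. It equals neither Section 11 tier, so it cannot be read as a restatement of the general rule. A report on day 5 (120 h), if that was the earliest practicable time, would meet Appendix J and breach Section 11.6. Neither Section 11.6 nor Appendix J says when the clock starts, so only the stated limits are compared.

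**The case against.** The case on the other side concerns weight, and much of it stands.

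- **Every item 9 rule that triggers an action uses 2 or more.** This covers exclusion, the pop-up and call-back offer, and the adverse event definition. The Appendix I wording repeats the Section 11.1 label almost exactly and is probably a slip.
- **Score-2 participants do not go unseen.** Appendix I has all adverse events reported to the Trial Management Group, provides a monthly safety report, and has the group review a template "which includes the number of call backs that were triggered, and the follow-up that was carried out". The call-back count is only a partial safeguard, because a call-back is generated only when the participant accepts the offer.
- **The stopping guideline is loose.** It gives no anticipated rate and no boundary, it is discretionary, and it is not confined to the listed endpoints. The group could act on score-2 cases however the endpoint is worded.
- **The two notification limits can both be met.** A prompt report inside 72 hours satisfies both texts. The mismatch concerns notification, not when the protective measure is taken.
- **Other provisions help.** Appendix I requires suspected unexpected serious adverse events or reactions to reach the group and the ethics committee within 24 hours. The provision on emerging safety issues has the group consult the ethics committee and the sponsor's delegate before it implements a plan. The 24-hour rule covers only that subset of events, so it does not settle the limit for urgent safety measures generally.
- **The safety flow chart in Section 11.7 is not visible in the text at hand.** Saying that nothing states which version governs therefore holds only for the visible text.

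These points limit the consequence. None of them reconciles the two thresholds or the two deadlines.

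**Conclusion.** Both inconsistencies hold, and both are minor. Appendix I counts one item 9 response category (score 3) where Sections 9.2 and 11.1 and Appendix J count two (scores 2 and 3). Taken literally, the endpoint rate in the stopping guideline omits participants scoring exactly 2 whom the register holds under the same label. Appendix J's outer limit for notifying an urgent safety measure is 168 hours against 72 hours in Section 11.6.

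The conclusion rests on reading each text as written. It does not claim that score-2 participants go unmonitored, that any safety measure would be delayed, or that the efficacy analysis is affected. The size of any undercount is unknown.

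**What to change.** Make two edits, each aligning an appendix with the main protocol.

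1. Appendix I, Safety analyses: replace the threshold of greater than 2 with *a score of ≥ 2 on item 9*.
2. Appendix J, Reporting Adverse Events: for a significant safety issue that requires an urgent safety measure, replace the 7-day limit with *within 72 hours*, and keep the instruction to report as soon as possible.

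The cost is wording only. Data collection, sample size and analysis do not change.
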